### **8.6.2 Analysis of the primary efficacy endpoint for US**

Mean change in Hb from baseline to the subjects mean level from week 28 to week 52 will be analysed with multiple imputation ANCOVA as described in the SAP. The model will contain

terms for the treatment, baseline Hb measurement, baseline eGFR, geographic region and CV history. Superiority of roxadustat compared to placebo will be declared, and this test as successful, if the lower bound of the 2-sided 95% confidence interval of the difference between roxadustat and placebo exceeds 0 g/dL. The ITT analysis set will be used.

### 8.6.3 Analysis of the primary efficacy endpoint for EU (Secondary Endpoint for FDA)

Hb response (Yes/No), where Yes is defined as:

- Hb  $\geq$  11.0 g/dL and Hb increase from baseline by  $\geq$  1.0 g/dL, for subjects with baseline Hb  $>$  8.0 g/dL; or
- Hb increase from baseline by  $\geq$  2.0 g/dL, for subjects with baseline Hb  $\leq$  8.0 g/dL

at two consecutive visits [dates] (with available data) separated at least 5 days during the first 24 weeks of treatment without having received rescue therapy (RBC transfusion, ESA, or IV iron) prior to Hb response. The first date of the two consecutive visits will be used as the date of response. The second date of the two consecutive visits will be used when evaluating the presence or absence of rescue therapy. The proportion of responders in the primary efficacy variable will be compared using a Cochran–Mantel–Haenszel (CMH) test adjusting for the region, history of CV, baseline Hb ( $\leq$ 8,  $>$ 8 g/dL) and baseline eGFR ( $\leq$ 30,  $>$ 30 mL/min/1.73 m^2), comparing roxadustat to placebo. The FAS will be used.

### 8.6.4 CV safety endpoint analyses

The CV safety evaluation strategy is to conduct pooled analyses of adjudicated data across the study program to ensure that the overall number of events is high enough to provide adequate power. Thus, all analyses of CV safety will be conducted in accordance with the PSAP.

### 8.6.5 Analysis of the secondary efficacy endpoints

Secondary efficacy endpoints will be tested using a fixed sequence approach to adjust for multiple testing. If the p-value from a test is less than 0.05, the test will be declared as successful and the analysis will continue to the next comparison in the sequence. Formal statistical hypothesis testing will be stopped as soon as a test is accompanied by a p-value  $\geq$ 0.05. The FAS will be used on the first secondary endpoint, OT+28 will be used for the two secondary endpoints related to rescue therapy, and the ITT analysis set will be used for all the remaining secondary endpoints.

1. The EU primary endpoint is the first secondary efficacy endpoint for FDA (see above)
2. Mean change in Hb from baseline to the subjects mean level from week 28 to week 52 in subjects with baseline hsCRP greater than the Upper Limit Normal (ULN) will be analysed analogously as the primary efficacy endpoint. Superiority of roxadustat compared to placebo will be declared, and this test as successful, if the lower bound of

the 2-sided 95% confidence interval of the difference between roxadustat and placebo exceeds 0 g/dL.

3. Proportion of total time of interpolated Hb values  $\geq 10$  g/dL from week 28 until week 52 will be estimated for each subject and used as dependent variable. The difference between roxadustat and placebo will be compared using ANCOVA with treatment group, geographic region and CV history as fixed factors and baseline Hb and baseline eGFR as covariates. Superiority between the groups will be declared, and this test as successful, if the lower bound of the 2-sided confidence interval of the difference between roxadustat and placebo exceeds 0.
4. Proportion of total time of interpolated Hb values within the interval 10-12 g/dL from week 28 until week 52 will be estimated for each subject and used as dependent variable. The difference between roxadustat and placebo will be compared using ANCOVA with treatment group, geographic region and CV history as fixed factors and baseline Hb and baseline eGFR as covariates. Superiority between the groups will be declared, and this test as successful, if the lower bound of the 2-sided confidence interval of the difference between roxadustat and placebo exceeds 0.
5. Mean change from baseline in LDL cholesterol to week 24 will be analysed using ANCOVA. Baseline Hb, baseline eGFR and baseline LDL will be used as covariates and treatment arm, CV history and geographic region as fixed effects. Superiority will be declared if the upper bound of the 2-sided 95% confidence interval of the difference between roxadustat and placebo exceeds 0.
6. Time-to-first (and proportion of subjects receiving) rescue therapy (composite) of any of IV iron, RBC transfusion or erythropoietin analogue as rescue therapy, will be analyzed using the Cox proportional hazard model with OT+28. Baseline Hb, baseline eGFR, geographic region, and CV history will be included as covariates. Superiority will be claimed, and this test successful, if the upper limit of the 2-sided 95% CI for the hazard ratio is less than or equal 1.0.
7. Time-to-first (and proportion of subjects receiving) RBC transfusion as rescue therapy, will be analyzed using the Cox proportional hazard model with OT+28. Baseline Hb, baseline eGFR, geographic region, and CV history will be included as covariates. Superiority will be claimed, and this test successful, if the upper limit of the 2-sided 95% CI for the hazard ratio is less than or equal 1.0.
8. Mean change in SF-36 Vitality (VT) sub-score from baseline to average VT sub-score of weeks 12-28 will be analyzed using MMRM with treatment, visit, treatment-by-visit interaction, and baseline covariates, including the baseline score, baseline Hb, baseline eGFR, and geographic region and CV history, as fixed effects and subject as a random effect. Superiority between roxadustat and placebo will be declared, and this test

successful, if the lower bound of the 2-sided confidence interval for the difference between roxadustat and placebo exceeds 0.

9. Annual rate of eGFR change in log scale prior to initiation of dialysis/kidney transplant will be estimated with MMRM using all post-baseline log (eGFR values) prior to initiation of dialysis/kidney transplant. Baseline eGFR in log scale, baseline Hb and geographic region, CV history, treatment group and post-baseline eGFR measurement time will be treated as fixed effects, and subject and time as random effects, i.e. random intercept and slope.
10. Mean change in SF-36 Physical Functioning (PF) sub-score from baseline to average PF sub-score of weeks 12-28 will be analyzed using MMRM with treatment, visit, treatment-by-visit interaction, and baseline covariates, including the baseline score, baseline Hb, baseline eGFR, and geographic region and CV history, as fixed effects and subject as a random effect. Superiority between roxadustat and placebo will be declared, and this test successful, if the lower bound of the 2-sided confidence interval for the difference between roxadustat and placebo exceeds 0.

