## **8.2 Sample size estimate**

Primary efficacy endpoint: A sample size of 450 subjects will have > 99% power to detect a 0.75 g/dL difference in mean Hb values between the two treatment groups, assuming that the common standard deviation is 1.2 g/dL, using an analysis of variance (ANOVA) test with a 0.05 two-sided significance level.

To contribute adjudicated CV safety events for the pooled CV analyses across the phase 3 program: approximately 2600 subjects are planned to be randomized in a 1:1 ratio to either roxadustat or placebo. The sample size in this study is driven by the overall requirement of adjudicated CV events for the phase 3 program in CKD-NDD (which consists of 3 studies in total targeting 465 subjects with MACE events). The two other placebo-controlled studies in the study program are FGCL-4592-060 and 1517-CL-0608.

Further information related to the sample size determination can be found in the study statistical analysis plan and the pooled statistical analysis plan.

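### The eGFR-slope test (item 9) has no direction in its success rule, so a significantly faster decline on roxadustat would count as a success and open test 10

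*Protocol*

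**What the plan says.** Protocol section 8.6.5 sets one gate for the whole sequence: "If the p-value from a test is less than 0.05, the test will be declared as successful". Testing then moves to the following item. The stopping rule mirrors it: "Formal statistical hypothesis testing will be stopped as soon as a test is accompanied by a p-value" of 0.05 or more. Neither rule mentions the sign of the estimate.

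Most items then add a condition of their own:

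- Items 2, 3, 4, 8 and 10 require the lower confidence bound of the roxadustat-placebo difference to lie above 0.
- Items 6 and 7 require the upper limit of the hazard ratio to be no greater than 1.
- Item 5 (LDL) also names a bound. Its wording is a separate matter.

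Item 9 differs. It says that the annual rate of change in log eGFR "will be estimated with MMRM using all post-baseline log (eGFR values) prior to initiation of dialysis/kidney transplant", lists the fixed and random effects, and ends. It gives no superiority statement, interval or direction.

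Item 1 is similar: "The EU primary endpoint is the first secondary efficacy endpoint for FDA (see above"). That points back to section 8.6.3, which specifies a Cochran-Mantel-Haenszel test "comparing roxadustat to placebo. The FAS will be used". No bound or direction is given there either.

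**The concern.** Where an item carries its own bound, that bound supplies the direction. Where it does not, the general p-value rule is the only criterion left. For item 9, a steeper eGFR decline on roxadustat with p below 0.05 fits the written definition of a successful efficacy test, and the sequence moves on to SF-36 Physical Functioning.

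This matters more for eGFR than for most endpoints in the list, because harm is possible. The secondary objective in section 2.2 is worded neutrally, as an effect on CKD progression compared with placebo, so it supplies no direction. Section 6.3.8 keeps CKD progression out of adverse event reporting. Item 9 is therefore the protocol's named comparison of CKD progression between arms, and its decision rule should not be able to label an adverse result a success.

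**Working it through.** **The plan's own figure.** The protocol gives no power, variance or effect size for the eGFR slope. Its only power statement (section 8.2) concerns the US primary Hb endpoint: 450 subjects, a difference of 0.75 g/dL, SD 1.2 g/dL, two-sided 0.05. Reading 450 as the total, SE = 1.2 × √(2/225) = 0.113, 0.75/0.113 = 6.63, and power is about Φ(6.63 − 1.96), which exceeds 99.99%. The stated figure of more than 99% is reproduced. The present point does not depend on it.

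**Sidedness.** Section 8.6.5 does not say whether its p-values are one- or two-sided. The two-sided reading rests on section 8.2 ("using an analysis of variance (ANOVA) test with a 0.05 two-sided significance level") and on the two-sided intervals in the other items. No one-sided test is stated in the sections on these analyses.

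**Set-up.** Let z be the estimated slope difference (roxadustat minus placebo) divided by its standard error. A negative value means faster loss on roxadustat. If the true harm is h standard errors, z is approximately normal with mean −h and variance 1. Then:

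- Passes in the wrong direction as written: P(z < −1.96) = Φ(h − 1.96).
- Passes in either direction as written: Φ(h − 1.96) + Φ(−h − 1.96).
- Passes with a lower-bound rule (bound above 0): P(z > 1.96) = Φ(−h − 1.96).

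**Results, all conditional on tests 1-8 having passed.** The values of h are assumptions.

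| True harm h (in SE) | Test 9 passes as written | of which wrong direction | Test 9 passes with lower-bound rule |
|---|---|---|---|
| 0 | 5.0% | 2.5% | 2.5% |
| 1.96 | 50% | 50% | 0.004% |
| 2.8 | 80% | 80% | 0.0001% |
| 3.24 | 90% | 90% | about 0% |

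For example, at h = 2.8, Φ(2.8 − 1.96) = Φ(0.84) = 0.80.

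**Effect on test 10.** Item 10 still needs its own lower bound above 0. If roxadustat has no effect on Physical Functioning, that happens with probability 0.025. At h = 2.8, and treating the two tests as independent for illustration, a false Physical Functioning claim then has probability 0.80 × 0.025 = 0.020. It cannot exceed 0.025, whatever happens at test 9.

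**The case against.** The strongest reply is that this is a drafting omission. The section concerns efficacy endpoints, seven of the ten items define success as superiority in roxadustat's favour, and no sensible reader would present renal harm as an efficacy win. The slope estimate would be reported with its sign, and laboratory changes are a secondary safety outcome, so an adverse result would be visible. Section 8.6 also leaves further detail to the SAP, which is not at hand and may state a direction.

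Much of this stands. The neighbouring items show that direction was intended, and nothing suggests a plan to credit harm. The SAP argument carries less weight: the protocol itself fixes the success rule and supplies bounds for the other tests, so item 9 is an inconsistency within a stated rule and not a detail left for later.

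A reader might infer four stronger things that the documents do not support:

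- **Type I error is inflated.** It is not. Two-sided familywise error stays at 5%: moving on after rejecting a false null is legitimate, and with no true effect the two tails together make up the 5%.
- **A wrong-direction pass yields a false claim for test 10.** It only opens that test, which must still succeed in roxadustat's favour.
- **The percentages are overall probabilities.** They apply only if tests 1-8 have all passed. They also cannot be converted to log-eGFR units without assuming a slope SD and a harm size, neither of which is in the protocol.
- **Item 1 is an equal problem.** Its wording has the same gap, but significantly fewer Hb responders on roxadustat than on placebo is unlikely, given that the trial is planned around a 0.75 g/dL difference in mean Hb.

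**Conclusion.** The point holds for item 9. As written, a significantly faster eGFR decline on roxadustat is a successful test and opens the last test in the sequence. Conditional on reaching test 9, this happens 2.5% of the time with no true effect, and about 50% and 80% of the time at true harms of 1.96 and 2.8 standard errors. These figures assume a two-sided p-value and an approximately normal estimate. They illustrate the rule and do not predict this trial.

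The consequence lies in what is called a success and what passes the gate. Error control and the US primary analysis, which has its own superiority bound in section 8.6.2, are unaffected. The text should be corrected, but the defect does not undermine the testing strategy.

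**What to change.** In section 8.6.5, change the general rule so that a test succeeds only if the two-sided p-value is below 0.05 and the estimate favours roxadustat.

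Add to item 9 that superiority is declared, and the test is successful, if the lower bound of the two-sided 95% confidence interval for the difference in annual log-eGFR slope (roxadustat minus placebo) exceeds 0. Identify that difference as the treatment-by-time contrast, because the terms now listed for item 9 do not name it.

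For consistency, the same direction wording can be added to the Cochran-Mantel-Haenszel test in section 8.6.3. The SAP should carry matching text.

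The cost is a few sentences. No data collection, sample size or operational step changes. Power to show a benefit is essentially unchanged, because a lower bound above 0 is the favourable half of the existing two-sided test.

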##### **7.7.1.1 Statins**

When coadministered with roxadustat, hydroxymethylglutaryl coenzyme A reductase inhibitor (statin) exposure was increased 2- to 3-fold. Investigators should consider this interaction and local prescribing information when deciding on the appropriate statin dose for individual patients, bearing in mind the impact of ethnicity, other concomitant medications, renal and hepatic function. Goals of lipid lowering treatment should be maintained as clinically indicated. The recommended maximum daily statin doses are: simvastatin 20 mg, atorvastatin 40 mg, rosuvastatin 10 mg, pravastatin 40 mg, fluvastatin 40 mg (20 mg if eGFR<30), pitavastatin 2 mg (1 mg if eGFR<30).

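### The LDL success rule is reversed: superiority is declared when the upper confidence limit exceeds 0, so a demonstrated LDL reduction fails and an LDL increase passes

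*Protocol*

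**What the plan says.** Protocol section 8.6.5 lists ten secondary endpoints tested in a fixed order. The general rule at its head is: "If the p-value from a test is less than 0.05, the test will be declared as successful". It continues: "Formal statistical hypothesis testing will be stopped as soon as a test is accompanied by a p-value" at or above 0.05. No direction of effect is named. On the analysis population, "the ITT analysis set will be used for all the remaining secondary endpoints", which includes LDL.

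Item 5 is LDL: "Mean change from baseline in LDL cholesterol to week 24 will be analysed using ANCOVA". Its success rule is: "Superiority will be declared if the upper bound of the 2-sided 95% confidence interval of the difference between roxadustat and placebo exceeds 0".

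The neighbouring items have the usual form. For rescue therapy and RBC transfusion (items 6 and 7), where lower is better, superiority needs the "upper limit of the 2-sided 95% CI for the hazard ratio is less than or equal 1.0". For SF-36 Vitality (item 8), where higher is better, the test is "successful, if the lower bound of the 2-sided confidence interval for the difference between roxadustat and placebo exceeds 0". Items 2, 3, 4 and 10 follow the same lower-bound pattern as item 8. All of these items also say that meeting the interval rule makes the test successful; item 5 does not.

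The LDL endpoint itself (sections 2.2 and 8.4.3) is given without a favourable direction.

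**The concern.** A superiority rule has to place the whole confidence interval on the favourable side of the null value. Item 5 does not do so in either direction. If lower LDL is the benefit, the upper limit must be below 0. If higher LDL were the benefit, the lower limit would have to be above 0. An upper limit above 0 shows neither; it shows only that a reduction has not been demonstrated.

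Item 5 also disagrees with the general p-value rule of the same section in two of the three possible outcomes, and the one outcome on which they agree is a significant rise in LDL. This is a test within a multiplicity-controlled sequence, in a study that the rationale for version 6.0 describes as pivotal for efficacy. Rescue therapy, RBC transfusion, SF-36 Vitality, eGFR slope and SF-36 Physical Functioning all follow it. A contradictory criterion at step 5 invites a dispute after unblinding about whether LDL was won and on what basis the later tests were reached.

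**Working it through.** **The plan's own figures.** The protocol gives no effect size, SD or power for LDL, so there is no LDL figure to reproduce. Its only power figure is for the primary Hb endpoint (section 8.2): 450 subjects, difference 0.75 g/dL, SD 1.2 g/dL, two-sided 0.05, power above 99%. With 225 per arm, SE = 1.2 × √(2/225) = 0.113 and 0.75/0.113 = 6.63. Power is Φ(6.63 − 1.96) = 0.999998, so that statement reproduces. The LDL point does not depend on it.

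**Outcomes side by side** (D = roxadustat minus placebo):

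| 95% CI for D | p<0.05 rule | Item 5 as written | Correct rule (lower is better) |
|---|---|---|---|
| wholly below 0 (LDL lowered) | successful | not superior | superior |
| crosses 0 | stop | superior | not superior |
| wholly above 0 (LDL raised) | successful | superior | not superior |

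**Probabilities.** Let Z = D/SE, approximately N(d, 1), where d is the true difference in SE units.

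- Item 5 alone: D + 1.96 SE > 0, that is Z > −1.96, so P = 1 − Φ(−1.96 − d).
- Correct rule: Z < −1.96, so P = Φ(−1.96 − d).
- Item 5 together with two-sided p<0.05: Z > +1.96, so P = 1 − Φ(1.96 − d).

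| True effect d | Item 5 alone | Correct rule | Item 5 and p<0.05 |
|---|---|---|---|
| +2 (LDL raised) | 1.000 | 0.000 | 0.516 |
| +1 | 0.9985 | 0.0015 | 0.1685 |
| 0 | 0.975 | 0.025 | 0.025 |
| −1.96 | 0.500 | 0.500 | <0.001 |
| −2.80 | 0.200 | 0.800 | <0.001 |
| −3.24 | 0.100 | 0.900 | <0.001 |
| −5 | 0.001 | 0.999 | <0.001 |

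The row d = 0 needs no assumption about LDL effect size or variability.

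**In SD units, over an assumed range.** About 2600 subjects randomized 1:1 gives 1300 per arm. If all are evaluable, SE = √(2/1300) = 0.0392 SD.

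| Evaluable per arm (assumed) | True reduction (assumed) | Item 5 alone | Correct rule |
|---|---|---|---|
| 1300 | 0.1 SD | 0.278 | 0.722 |
| 1300 | 0.2 SD | 0.001 | 0.999 |
| 780 | 0.1 SD | 0.494 | 0.506 |
| 780 | 0.2 SD | 0.023 | 0.977 |

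The clearer the true reduction, the less likely the written rule is to recognise it.

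**The case against.** The best defence is that the p-value rule governs the sequence. It says when testing stops, and item 5 is the only interval rule that does not mention success of the test. On that reading item 5 decides only the label of superiority, a null LDL result ends formal testing, and the figure of 0.975 describes a sentence that would never be applied alone. This stands in part. The p-value rule does prevent a null LDL result from opening items 6 to 10, and the 0.975 should be read beside the 0.025 under the joint rule. But the joint rule leaves only significant LDL increases as superior. The p-value rule alone, having no direction, also lets an increase through.

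It is also fair that the favourable direction is inferred. The statin guidance in section 7.7.1.1 ("Goals of lipid lowering treatment should be maintained as clinically indicated") is about managing co-medication and does not define the endpoint. The finding does not need the inference, because the written rule fails as a superiority criterion in both directions. Reading the difference as placebo minus roxadustat does not help either: the lower limit would then have to exceed 0.

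Two limits on the claim are accepted. The reduction that the rule rejects is a statistically demonstrated one; a true reduction whose interval crosses 0 would be called superior under item 5 alone. And the text is very probably a slip that the SAP, not examined here, may already state correctly. Section 8.6 leaves further detail to the SAP, but the protocol fixes this threshold itself.

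**Conclusion.** The concern holds. The LDL criterion in the current section 8.6.5 is the complement of a valid lower-is-better rule, and nothing else in the protocol corrects it. Taken alone it declares superiority with probability 0.975 under no effect, against 0.025 for the correct rule, and in 10% rather than 90% of trials at a true reduction of 3.24 SE. Combined with p<0.05 it recognises only LDL increases. These figures rest on a normal approximation and on the difference being roxadustat minus placebo; only the SD-unit illustrations use assumed effect sizes and evaluable numbers. The primary endpoints, sample size and data collection are not affected. It must be corrected because it is a wrongly fixed decision threshold inside the confirmatory testing sequence.

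**What to change.** Replace the last sentence of item 5 in section 8.6.5 with: *LDL superiority is claimed, and the test counts as successful, when the upper 95% confidence limit (two-sided) for roxadustat minus placebo is below 0.* This also restores the link to the sequence that the other interval rules carry.

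In the opening paragraph of section 8.6.5, add that a test passes only if p is below 0.05 and the estimated effect favours roxadustat. Without this, a significant LDL increase would still pass the general rule.

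State the favourable direction (a decrease) where the endpoint is defined in section 8.4.3, and check that the SAP uses the same rule. The cost is a few lines of text before unblinding, with no change to data, analysis model or sample size.

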### 2.2 Secondary objectives

Secondary Efficacy Objectives:	Outcome Measure:
The efficacy of roxadustat compared to placebo based on Hb response and level during the study	Proportion of total time of Hb $\geq$ 10 g/dL from week 28 to week 52. Proportion of total time of Hb within the interval of 10-12 g/dL from week 28 to week 52
The efficacy of roxadustat compared to placebo based on Hb response in inflamed subjects	Mean change in Hb from baseline to the subjects mean level between week 28 to week 52 in subjects with baseline high-sensitivity C-reactive protein (hsCRP) greater than the Upper Limit Normal (ULN)
The effect of roxadustat compared to placebo on Low-density lipoprotein (LDL) cholesterol	Mean change in LDL cholesterol from baseline to week 24
The need for rescue therapy in subjects treated with roxadustat as compared to placebo	Time-to-first (and proportion of subjects receiving) instance of receiving intravenous (IV) iron, red blood cell (RBC) transfusions, or erythropoietin analogue as rescue therapy. Time-to-first (and proportion of subjects receiving) instance of receiving red blood cell (RBC) transfusions as rescue therapy.
The effect of roxadustat on anemia symptoms and health-related quality of life (HRQoL) based on comparison with placebo	Changes in generic HRQoL as measured by the SF-36 (Version 2, standard)
The effect on the CKD progression of roxadustat as compared to placebo	Annual rate of eGFR change in log scale, calculated as the linear slope of log (eGFR values) to prior to initiation of dialysis/kidney transplant

Secondary Safety Objectives:	Outcome Measure:
To evaluate the safety and tolerability of roxadustat.	Adverse events (AEs), serious adverse events (SAEs). Changes in vital signs, electrocardiogram (ECG) and laboratory values.

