#### 8.4.6 CKD progression related secondary efficacy endpoints

To evaluate the effect of roxadustat on the CKD progression prior to initiation of dialysis/kidney transplant, the following variable will be analyzed:

- Annual rate of eGFR change in log scale, calculated as the slope of log (eGFR values), prior to initiation of dialysis/kidney transplant

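### The eGFR-slope model in step 9 of the fixed sequence has no treatment-by-time term, so it cannot estimate or test a difference in slope

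*Protocol*

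**What the plan says.** The secondary objective in Protocol section 2.2 is comparative: "The effect on the CKD progression of roxadustat as compared to placebo". Section 8.4.6 defines the variable as a slope: "Annual rate of eGFR change in log scale, calculated as the slope of log (eGFR values), prior to initiation of dialysis/kidney transplant".

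Section 8.6.5, item 9, says this rate "will be estimated with MMRM using all post-baseline log (eGFR values) prior to initiation of dialysis/kidney transplant". It then writes out the terms. The fixed effects are baseline log eGFR, baseline Hb, region and, in the protocol's words, "CV history, treatment group and post-baseline eGFR measurement time will be treated as fixed effects, and subject and time as random effects"; the random part is spelled out as a random intercept and slope. The item ends there, with no contrast, direction or confidence-interval criterion.

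Items 8 and 10, the SF-36 models on either side of it, are specified with "treatment, visit, treatment-by-visit interaction, and baseline covariates".

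The endpoint is formally tested. According to the opening of section 8.6.5, "Secondary efficacy endpoints will be tested using a fixed sequence approach to adjust for multiple testing", and "If the p-value from a test is less than 0.05, the test will be declared as successful". Item 9 is the ninth of ten steps, on the ITT set.

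**The concern.** An effect of treatment on a slope is an interaction between treatment and time. A model with only main effects for treatment and time has no parameter for it. The remaining treatment coefficient measures a constant offset in log eGFR, which is a different question from how fast kidney function declines.

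If that coefficient supplies the p-value for step 9, two errors follow. A constant offset could be reported as slower progression, even when decline is faster on drug, and a real difference in progression could be missed. Because no direction is stated, a significantly worse result would, read literally, also count as a success and open step 10.

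**Working it through.** **The plan's own figure.** The protocol gives no power or effect size for the eGFR slope. Its only power statement (section 8.2) concerns the primary Hb endpoint: 450 subjects, difference 0.75 g/dL, SD 1.2 g/dL. It reproduces: z = 0.75 / (1.2 × √(2/225)) = 6.63, and Φ(6.63 − 1.96) = 0.999998, which is above 99%. It has no bearing on item 9.

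**Algebra of the listed model.** For subject i at time t (years):

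log eGFR = covariates + b1·treatment + b2·t + u0i + u1i·t + error, with u0i and u1i of mean zero.

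- Mean slope on placebo: b2.
- Mean slope on roxadustat: b2.
- Difference in slope: b2 − b2 = 0, whatever the data show.
- b1 is a shift in level that is the same at every visit.

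The random slope does not help. It lets patients vary around the common b2 but gives the arms no separate means. With b3·treatment·t added, the difference in slope is b3.

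**Size under assumed values.** From the protocol: about 2600 subjects randomised 1:1, so 1300 per arm; visits every 2 weeks to week 20, every 4 weeks to week 52, then every 8 weeks. Assumed, because the documents do not give them: an eGFR value at every visit, a two-year horizon, and log-scale SDs of 0.10–0.15 (intercept), 0.15–0.25 per year (slope) and 0.10–0.12 (residual). The method is generalised least squares with V = ZGZ′ + σ²I, comparing X = [1, treatment, t] with X = [1, treatment, t, treatment·t]. Two-sided rejection is Φ(z − 1.96) + Φ(−z − 1.96), where z = estimate/SE.

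Example with SDs 0.10 / 0.15 / 0.12:

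| Truth | Tested term | Estimate (SE) | z | Rejection |
|---|---|---|---|---|
| Slope difference 0.03/year, no shift | treatment (as written) | 0.0017 (0.0042) | 0.40 | 0.060 + 0.009 = 0.069 |
| Same | treatment × time | 0.030 (0.0061) | 4.92 | 0.998 |
| Level shift 0.02, equal slopes | treatment (as written) | 0.020 (0.0042) | 4.76 | 0.997 |
| Same | treatment × time | 0 (0.0061) | 0 | 0.05 |

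Across the assumed SD ranges:

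- Slope difference 0.03, no shift: 5–7% as written, about 86–99.8% with the interaction.
- Level shift 0.02–0.03, equal slopes: 91–100% as written, 5% with the interaction.
- Level shift +0.03 with slope −0.03 per year (faster decline on drug): a significant positive treatment coefficient in over 99% of trials as written.

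**Independent check by simulation.** Mixed models were fitted to 400 subjects, 11 visits over about two years, SDs 0.15 / 0.15 / 0.10, with 40 runs per scenario. The Monte Carlo standard error is about √(0.05 × 0.95/40) = 0.034 at a 5% rate.

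- True slopes −0.20 and −0.15, no shift: as written, one common slope of −0.176 and a treatment coefficient of 0.005, rejected in 5%. With the interaction, 0.049, rejected in 90%.
- Equal slopes, shift 0.05: as written, 0.049, rejected in 92.5%. With the interaction, −0.003, rejected in 5%.

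**Success rule.** Items 2–8 and 10 each state a confidence-bound criterion; item 9 states none. The general p < 0.05 rule is then all that applies.

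**The case against.** Four points can be made for the plan.

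1. **Item 9 never says the treatment main effect is tested.** Sections 2.2 and 8.4.6 call for a slope, so the term list may simply be incomplete, and section 8.6 leaves further detail to the SAP, which was not available for this review. That is possible. But the protocol writes the terms out one by one, and the neighbouring items name their interactions. An SAP that includes the term would be correcting the protocol, and the two would still need aligning.

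2. **The sizes depend on the assumptions.** This stands. With 4-weekly values to week 52 and 8-weekly after that, the as-written rejection of a 0.03 slope difference, at intercept SD 0.10 and residual SD 0.12, is:

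| Slope SD per year | About two years | 52 weeks |
|---|---|---|
| 0.15 | 9% | 26% |
| 0.08 | 40% | 71% |
| 0.05 | 87% | 89% |

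The opposite-sign scenario falls to 63% (SDs 0.15/0.05/0.15) or 79% (0.20/0.10/0.15) over two years. Follow-up will also vary: the version history expects up to 4 years for some patients, and data stop at dialysis or transplant. The model as written is therefore not always blind to a slope difference. Where it does react, it still does so through a coefficient that is not the slope difference.

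3. **The missing direction rule is a separate gap and not unique.** Item 1, the CMH test, also states no direction. This is correct, and the consequence for item 9 is limited to opening step 10.

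4. **Position.** Step 9 is reached only if the eight steps before it succeed, and the primary endpoints, the pooled CV safety analysis, the sample size and data collection are unaffected. This limits the reach of the error but does not make the model right.

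**Conclusion.** The point holds. As written, item 9 cannot estimate or test the endpoint defined in section 8.4.6, because the between-arm difference in slope is fixed at zero. That follows from the listed terms alone.

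The practical size rests on assumed eGFR variances, visit times and follow-up. Under the main assumptions the as-written test has close to no power for a real slope difference and near-certain rejection for a small constant offset. With small between-patient slope variation or one-year follow-up, its sensitivity to a slope difference can rise to about 89%. The misreading of a level shift as a progression effect remains.

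This is a multiplicity-controlled test of a progression claim, so it should be corrected before database lock, even though it comes late in the sequence. The missing direction rule is a lesser fault that the same edit can repair.

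**What to change.** In section 8.6.5, item 9, and in the SAP:

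- Add treatment-by-time as a fixed effect, keeping the random intercept and slope.
- Name its coefficient, the roxadustat-minus-placebo difference in annual log-eGFR slope, as the tested quantity.
- Add a success rule: superiority is claimed only if the lower limit of the two-sided 95% confidence interval for that difference is above 0.

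If the SAP already has the interaction, align the protocol text with it. The cost is one model term and one sentence in each document, with no new data and no change to study conduct. Section 8.6 requires the SAP to be final only by database lock, so the change can be made while the analysis team is still blinded.
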